advised to continue ad lib (according to their own choice) diet. At the very 1st day of the study, the spirometric lung functions will be assessed by measuring forced vital capacity (FVC), forced expiratory volume in 1st second (FEV₁), forced expiratory ratio (FEV₁/FVC%), peak expiratory flow rate (PEFR) and forced mid expiratory flow of FVC (FEF_{25-75%}), maximum expiratory flow₇₅ (MEF₇₅), maximum expiratory flow₅₀ (MEF₅₀), maximum expiratory flow₂₅ (MEF₂₅) with a portable digital spirometer with a portable digital spirometer. In addition, exercise tolerance will be assessed by change in 6 minute walk distance (6MWD) in 6 minute walk test (6MWT). Changes in peripheral capillary oxygen saturation (SpO₂) by Pulse Oximeter and degree of dyspnea and fatigue by Modified Borg Scale (MBS) will also be measured both before and after 6MWT, to evaluate their changes in both the groups. All these variables will be again measured on their follow-up in 13 weeks and 26 weeks with standard pharmacological treatment of ACO with D₃ intervention (B group) and also without D₃ intervention (A group). The data will be statistically analyzed by Graphpad prism (Version 7) using independent sample 't' test (between two groups), paired Student's 't' test (between paired groups before and after intervention). Group comparisons will be done using one way ANOVA. In the interpretation of results, ≤0.05 level of probability (p) will be accepted as significant.

Expected outcome of the study:

- Impaired lung functions and exercise tolerance in vitamin D₃ deficient ACO patients will be detected and the good impact of vitamin D₃ supplementation for six months on restoration of the lung function status and exercise tolerance in ACO patients will be proved.

Key words: Asthma COPD Overlap, Vitamin D₃, FVC, FEV₁, FEV₁/FVC%, FEF_{25-75%}, PEF_R, MEF_{75%}, MEF_{50%}, MEF_{25%}, SpO₂, 6 Minute Walk Distance, Modified BORG scale.

Introduction

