Is there any improvement in lung function status and exercise tolerance in vitamin D₃ deficient ACO patients after having vitamin D₃ supplementation?

Hypothesis

Null: Vitamin D₃ supplementation does not improve lung functions and exercise tolerance in vitamin D deficient ACO patient.

Alternate: Vitamin D₃ supplementation improves lung functions and exercise tolerance in vitamin D deficient ACO patient.

Objectives:

General objectives:

To evaluate the effects of vitamin D₃ supplementation on lung function status and exercise tolerance in D₃ deficient, stable patients with ACO.

Specific objectives

- To measure the FVC, FEV₁, FEV₆, FEV₁/FVC%, PEFR and FEF_{25-75%} of vitamin D₃ deficient, stable patients with ACO, in order to assess their lung function status at baseline.
- To measure the 6MWD of all the patients, in order to assess their functional exercise capacity at baseline.
- To measure the SpO₂ at rest of all the patients, in order to assess the basal oxygenation status at baseline.
- To measure the level of dyspnea and fatigue at rest of all the patients in order to assess the basal breathlessness level at baseline.
- To measure the both the SpO₂ and level of dyspnea and fatigue again after 6MWT, for the assessment of their exercise tolerance at baseline.
- To measure the all these variables in study group at 13th weeks and at 26th weeks of their follow up.
- To measure the all these variables in control group at 13th weeks and at 26th weeks of their follow up.
- To compare all these variables in study group at baseline and endline.
- To compare all these variables in control group at baseline and endline
- To compare all these variables in both group at baseline and endline.

Methods

Type of study	: Double blinded placebo controlled trial
Place of study	: Department of Physiology, Bangabandhu Sheikh Mujib Medical University (BSMMU), Shahbagh, Dhaka
Period of study	: March 2018 to February 2019
Study population	: Stable patients of ACO with vitamin D ₃ deficiency
Sample size	: 60
Sampling	: Consecutive sampling
Grouping	:
Group A (Control)	: 30 (thirty) D ₃ deficient ACO patients with placebo administration
Group B (Study)	: 30 (thirty) D ₃ deficient ACO patients with vitamin D ₃ administration

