If the patient with D₃ deficiency [Serum 25(OH)D <30 ng/ml] and not with renal insufficiency (Serum creatinine >1.3 mg/dl), then the Fasting blood sugar, serum HbA_{1c}, serum parathormone (PTH), serum calcium (Ca²⁺), serum phosphate (PO₄³⁻), serum alkaline phosphatase (ALP), serum SGPT, serum cholesterol, serum High Density Lipoprotein (HDL), serum low density lipoprotein (LDL), serum triglyceride (TG), will be assessed from the preserved blood.

After that their height and weight will be measured and the spirometric lung function test will be done by using a portable spirometer (PONY FX, cosmed, Italy]. After getting all the biochemical and spirometric reports the final selection will be done, according to the inclusion and exclusion criteria. All the eligible patients will be randomly assigned to either 'Control' or 'Study' groups and will be thoroughly informed about the objectives and detailed study procedure, once again.

Subsequently a standard therapeutic treatment (according to GOLD guideline) will be prescribed to all the selected stable ACO patients of both groups. Proper education will be given about drug, method of taking medication and medication plan.

Along with the standard pharmacological treatment of ACO, the patients of the 'Study group' will be prescribed for 80,000 IU/ week of oral vitamin D₃, for consecutive 13 weeks. Subsequently, all the patients will be cordially requested to again visit the Department of physiology, BSMMU, on 13th week of their follow up to reexamine all the study

variables along with serum 25(OH)D and Ca^{2+} (to check the toxicity). These data will be recorded as values of '13th week' (B13).

Then according to serum level of 25(OH)D and Ca^{2+} (American Vitamin D council 2017), 40,000 IU / 1 to 6 week oral vitamin D₃ will be prescribed, for further 13 weeks. At 26th week of follow up, they will be requested again to visit the Department of Physiology, BSMMU, to reexamine all the study variables, and the data will be recorded as values of '26th week' (B26).

Similarly, all the patients of 'control group' will be prescribed for placebo (along with standard pharmacological treatment of ACO, prescribed by pulmonologist) for consecutive 26 weeks and their respective data will be recorded as A13 and A26.

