With these, all patients of both the groups will be advised to continue ad lib (according to their own choice) diet as well as to have sunlight exposure (within 10 am to 2 pm) only for 20 minutes daily (Manjeeta 2016).

In the mean time, a good rapport will be built up to take time to time follow-up over telephone and visiting patient's place with scheduled appointment to maintain a proper follow up at 1st (day 1) 2nd (at 13th week) and 3rd (at 26th week) visit of the study , in addition to the hematological values.

Any patient, who will be failed to follow the study procedure exactly during study period, will be dropped and a new one will be included to fulfill the desired total sample number.

Test procedure for spirometry

(Hassan 2018)

- At first, the subject will be asked to take rest sitting on a chair and remain calm and quiet for 5 minutes.
- The detailed procedure will be explained to him to ensure his maximum cooperation.
- The switch of spirometer will be on and windows will be open.
- Patients' information will be filled up and saved.
- The patient will be asked to hold a disposable paper mouthpiece (connected to spirometer) in his hand horizontally and to place it in between his two lips.
- To make good seal, he will also be asked to put the lips tightly around the outside of the mouthpiece.
- Then he will be asked to inhale first as deeply and as rapidly, as possible, which was followed by a forceful expiration for the possible longest period into the mouthpiece.
- The readings of different variables will be recorded from the spirometer monitor.
- Three (3) consecutive readings at 5 minutes interval for each parameter will be taken and the best value will be noted.

Test procedure for pulse oximetry

(Hassan 2018)

- The patient will be asked to take rest and remain calm and quiet for 10 minutes (MacAllister et al. 2007).
- The detailed procedure will be explained to him to ensure his maximum cooperation.
- Then his right index finger will be washed with alcohol and pulse oximeter sensor will be applied.
- The switch button will be on.
- The reading will be recorded from the display screen.
- Three (3) consecutive readings at 5 minutes interval will be taken and the best value will be noted.

Procedure for six minute walk test (6MWT)

(Hassan 2018)

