The 6MWT will be performed at indoors, along a long, flat, straight, enclosed corridor with a hard surface that was seldom traveled. The walking course will be 30 meter in length which was marked every 3 meter. The turnaround points will be marked with a cone. A starting line, which marked the beginning and end of each 6 meter lap, will be marked on the floor using brightly colored tape.

The subject will be asked to walk at his own maximal pace along the corridor from the end, covering as much ground as he can, during the allotted time, without running. He will be also advised to take rest if he

was too exhausted to continue the test. Standard phrases at regular intervals (every 60 seconds) will be used, like: “you are doing well,” “keep up the good work”. At the same time he will be also informed about the past time and how much left before the test completed.

If any of the subjects develop chest pain, intolerable dyspnea, leg cramps, staggering, diaphoresis or pale appearance the test will be immediately stopped and the subject will be dropped. Again, when any subject will complete the total test procedure (according to the exact protocol), he will be congratulated for good effort.

Vitamin and placebo administration

	Vitamin D₃	Placebo
Collection	Beximco Pharmaceuticals Limited, Bangladesh	Beximco Pharmaceuticals Limited, Bangladesh
Dose	80,000 IU/wk	80,000 IU/wk
Route	Oral	Oral
Ingredient	
• Cholecalciferol (40,000IU)• Microcrystalline Cellulose (58.1 gm)• Butylated Hydroxy Toluene (0.2mg)• Magnesium Stearate (3mg)• Gelatin Capsule Shell (1mg)	
• Microcrystalline Cellulose (303.8gm)• Butylated Hydroxy Toluene (0.2mg)• Magnesium Stearate (3mg)• Gelatin Capsule Shell (1mg)

STATISTICAL ANALYSIS

TITLE

**Effects of vitamin D₃ supplementation on lung functions and
exercise tolerance in D₃ deficient Asthma COPD Overlap
(ACO) patients**

Date: 06/09/2018

The results will be expressed as mean with standard error (mean \pm SE). The data will be statistically analyzed by Graphpad prism (Version 7) using independent sample 't' test (between two groups), paired Student's 't' test (between paired groups before and after intervention). Group comparisons will be done using one way ANOVA. Correlations between variables will be tested with Pearson correlation coefficient.

In the interpretation of results, ≤ 0.05 level of probability (p) will be accepted as significant.

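### Randomised patients who do not follow the procedure exactly are dropped and replaced, so every between-group comparison is made in patients selected on adherence

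*Combined protocol and SAP*

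**What the plan says.** **Order of events.** Under Study procedure, allocation follows final selection: "All the eligible patients will be randomly assigned to either" the control or the study group. Treatment and follow-up come afterwards, with visits at weeks 13 and 26. The same section then sets the rule: "Any patient, who will be failed to follow the study procedure exactly during study period, will be dropped and a new one will be included". Its stated purpose is "to fulfill the desired total sample number". It applies throughout the study period, so it acts on randomised patients.

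**Analysis.** The Statistical Analysis section names t tests, ANOVA ("Group comparisons will be done using one way ANOVA") and Pearson correlation. It gives no analysis set, no intention-to-treat principle and no method for missing data. The Project Summary adds none.

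**What must be followed.** No threshold for exact compliance is given. The data schedule in Appendix II has no field for capsules taken, although it records serum 25(OH)D at three time points. In the second half of the trial, study-group capsules "will be prescribed, for further 13 weeks" at an interval that depends on blood results. The text does not say whether placebo changes in parallel.

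**Walk test.** If listed symptoms occur during the 6MWT, "the test will be immediately stopped and the subject will be dropped". The section does not say from what he is dropped, or at which visit. The Project Summary has the test repeated: "All these variables will be again measured on their follow-up in 13 weeks and 26 weeks". Appendix II provides fields for a test stopped or paused early, the reason, the partial lap and end-of-exercise symptoms.

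**The concern.** Randomisation makes the two groups comparable at allocation. Removing patients for what they do afterwards, and filling the gaps with others, gives up that protection for every outcome. If adherence is related to prognosis or tolerability and is lost differently in the two arms, the difference can be biased either way. If it is lost equally, the result still answers a narrower question, the effect in men who complied, and not the effect of assigning vitamin D.

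Three features make this rule worse than an ordinary completer analysis:

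- With no definition of exact compliance, who is dropped is a matter of judgement.
- Replacement restores the total, so the final count hides the losses, and nothing in the readable text requires drops to be reported by arm.
- The text does not say whether a replacement is newly randomised or takes the vacant place.

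If placebo is not altered in parallel after week 13, what patients must follow may also differ by arm, even under blinding.

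**Working it through.** **Inputs.** From Sample size calculation: means 364.1 and 357.3, SDs 7.21 and 12.25, z values 1.96 and 0.84. The outcome is not named there, so 6.8 serves only as a scale. The documents give no drop rates or correlations; all of those below are assumptions.

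**1. The plan's own figure.** n = (1.96 + 0.84)² × (7.21² + 12.25²) / 6.8² = 1584.05 / 46.24 = 34.26, so 35 per group. It reproduces. The root-mean-square SD is √(202.05/2) = 10.05, and 6.8/10.05 = 0.68 SD.

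**2. A different quantity, even without bias.** Suppose a fraction d of the study group does not adhere, gains nothing and otherwise resembles the rest. The effect of assigning vitamin D is 6.8 × (1 − d):

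- d = 10%: 6.12
- d = 20%: 5.44

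Drop-and-replace still estimates 6.8, which is 1/0.9 = 1.11 or 1/0.8 = 1.25 times as large.

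**3. Bias with no true effect.** Let adherence correlate ρ with outcome, with a common SD of 10.05, and refill each arm to 35. Dropping the least adherent fraction p raises the retained mean by ρ·L(p) SD, where L(p) = φ(z_p)/(1 − p). L(10%) = 0.195, L(20%) = 0.350, L(30%) = 0.497. Type I error is from the noncentral t on 68 df.

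| Drops | ρ | Shift (SD) | On the 6.8 scale | Type I error |
|---|---|---|---|---|
| Equal | any, same in both arms | 0 | 0 | 5.0% |
| 10% vs 20% | 0.2 | 0.031 | 0.31 (5%) | 5.2% |
| 10% vs 20% | 0.5 | 0.078 | 0.78 (11%) | 6.2% |
| 10% vs 30% | 0.5 | 0.151 | 1.52 (22%) | 9.5% |

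The sign depends on which arm loses more.

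**4. Walk-test rule, only if it applies at follow-up and removes data.** Take a true benefit of 6.8, one symptom threshold for both arms and 10% control drops. Fewer study patients cross the threshold, so the bias is toward the null. At symptom-outcome correlations of 0.3 and 0.5 the expected difference is 6.6 and 6.4, and simulated power is 79% and 77%, against about 80% with no drops. At the extreme correlation of 1 it is 5.4, with power 71%.

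**5. Is replacement feasible?** The study period is "March 2018 to February 2019". If follow-up must fit within it, a 26-week (182-day) patient must start by 30 August 2018. A man dropped at week 13 can then be replaced only if he started 91 days earlier, by 31 May 2018. One dropped at week 26 must have started on 1 March 2018.

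**The case against.** The strongest reply is that the numbers are modest and assumed. With equal drops and equal correlations there is no bias, and telephone and home follow-up should keep drops few. If refilling is mostly impossible within the study period, the illustrations that assume it slightly overstate the type I error. The 11% and 25% are a gap between two questions, and the research question can be read as asking about men who took the supplement. Step 3 uses one SD. With the planned unequal SDs, equal 10% drops at ρ = 0.5 would still shift the difference by 0.5 × 0.195 × (12.25 − 7.21) = 0.49. The rule also never says in terms that collected data are discarded.

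Most of this stands as a limit on the illustrations and does not rescue the rule. Replacing a man to reach the desired total makes removal from the analysed sample the natural reading. An adherent-only question would still need adherence defined, and drops reported by arm. Serum 25(OH)D is only a partial marker of adherence. Some pages were not available for this review, so an offsetting statement there cannot be excluded; nothing in the available text limits the rule.

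**Conclusion.** The concern holds, and the rule must be changed. The plan as written compares groups selected after randomisation, for every outcome. That conclusion rests on the text and not on the illustrative figures. The true size and direction of bias are unknown: in the cases shown it runs from zero to 0.15 SD, with type I error from 5.0% to 9.5%, depending on assumed drop rates and correlations. Outcomes not collected from dropped patients cannot be recovered at analysis, so the correction is needed while they can still be followed.

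The walk-test point is one of clarification only. The 6MWT section and the Appendix II form must be reconciled.

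**What to change.** 1. **Study procedure.** Delete drop-and-replace for randomised patients. State that all randomised patients are analysed in their assigned group using all data collected, whatever their adherence, and that week-13 and week-26 outcomes are sought from everyone who has not withdrawn consent, except any test the responsible physician judges should not be done. Any additional recruits are newly randomised, and nobody is removed.
2. **6MWT section.** Leave the test-stopping rule alone. State that *dropped* does not remove the patient's data, and that distance to the stop, SpO₂, Borg scores and reason are analysed. Whether he continues or repeats the test is a clinical decision, not addressed here.
3. **Statistical Analysis and Project Summary.** Make the all-randomised set primary, with a stated method for missing data; a mixed model on baseline, week-13 and week-26 values would serve. Keep the adherent comparison as a sensitivity analysis, with adherence defined in advance and recorded on the form. Report drops and reasons by arm.
4. **Sample size.** Restate power without replacement, and settle the target, since the Project Summary gives 70 and Methods gives 60.

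**Cost.** Some rewording, one form field, extra follow-up and a less favourable stated power. By the plan's formula, power = Φ(D/√(202.05/n) − 1.96):

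| Case | 10% | 20% |
|---|---|---|
| 35 per group, outcomes lost (n = 31.5 or 28, D = 6.8) | 77% | 72% |
| 35 per group, non-adherers analysed with no gain (D = 6.12 or 5.44) | 72% | 62% |
| Same dilution, 39 or 44 per group | 77% | 72% |

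The starting point is 81% at 35 per group, or 75% at the 30 in Methods. Under the dilution in the second row, 80% needs 34.26/0.81 = 42.3, so 43 per group, or 34.26/0.64 = 53.5, so 54. Part of this is not new: finishing with 70 under the current rule already means randomising 70/0.9, about 78, or 70/0.8, about 88. The third row is the power if all of those are analysed.

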For the assessment of all the variables of all the patients on day 0, at 13th week and as well as at 26th week, they will be designated as A₀, A₁ and A₂ (control) and B₀, B₁ and B₂ (study). In addition, for the mean of SpO₂, level of dyspnea and level of fatigue at resting condition (before 6MWT), all the groups will be further designated as A_{0before}, A_{1before}, A_{2before}, B_{0before}, B_{1before} and B_{2before} respectively. Similarly after 6MWT all these six subgroups will be again designated as A_{0after}, A_{1after}, A_{2after} and B_{0after}, B_{1after}, B_{2after}, for measurement of these three variables.

Sample size calculation

Using the following statistical formula

$$n = [(Z\alpha + Z\beta)^2 \times (\sigma_1^2 + \sigma_2^2)] / (\mu_1 - \mu_2)^2$$

(Kirkwood and Sterne 2003)

$$\text{Mean of control, } \mu_1 = 364.1$$

$$\text{Mean of study group, } \mu_2 = 357.3$$

$$\text{SD of control, } \sigma_1 = 7.21$$

$$\text{SD of study group, } \sigma_2 = 12.25$$

(Hassan 2018)

$$\text{Type I Error, } Z\alpha = 1.96$$

$$\text{Type II Error, } Z\beta = 0.84$$

(Kirkwood and Sterne 2003)

Therefore,

$$\begin{aligned} n &= [(Z\alpha + Z\beta)^2 \times (\sigma_1^2 + \sigma_2^2)] / (\mu_1 - \mu_2)^2 \\ &= [(1.96 + 0.84)^2 \times (7.21^2 + 12.25^2)] / (364.1 - 357.3)^2 \\ &= [7.84 \times (51.9841 + 150.0625)] / (6.8)^2 \\ &= 1584.04534 / 46.24 \\ &= 34.2570359 \\ &= \text{approximately 35 for each group.} \end{aligned}$$

Subject selection:

Inclusion criteria

- Pulmonologist diagnosed stable patient of ACO
(GINA and GOLD 2015)
- Duration of ACO: > 4 year
- Vitamin D₃ deficient : Serum 25(OH)D <30 ng/ml
(Vitamin D Council 2017)
- Age: 40 -70 years
- Sex: Male
- Socioeconomic status: middle class
- Smoker
- Anthropometric status:
 - BMI=18.6-24.9 kg/m²
(WHO 2006)
 - mid upper arm circumference>25.1 cm
(Sultana et al. 2015)
 - waist-hip ratio<0.89
(Sultana et al. 2015)
- Serum parathormone: 10-65 pg/ml
- Serum Ca²⁺: 8.5-10.5 mg/dl
- Serum PO₄³⁻: 2.3-4.7 mg/dl
- Serum alkaline phosphatase: 30-120 U/L
- SGPT: <50 U/L
- Serum creatinine: 0.7-1.3 mg/dl
- FBS: 3.5-6.1 mmol/L
- Serum HbA1c: 4.5-6.3 %

- Serum cholesterol: <200 mg/dl
- Serum HDL: >40 mg/dl,
- Serum LDL: <130 mg/dl
- Serum TG: <150 mg/dl

Exclusion criteria

With history of:

[figure not shown]
- any other pulmonary diseases, as,
 - ✓ chronic obstructive pulmonary disease
 - ✓ bronchial asthma
 - ✓ respiratory tract infection
 - ✓ bronchiectasis
 - ✓ pleural effusion
 - ✓ tuberculosis

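### As written, the only SpO2 procedure (10 minutes of rest, then the best of three readings) would also apply after the 6MWT and would largely mask exertional desaturation

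*Combined protocol and SAP*

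**What the plan says.** The Project Summary states that SpO2, dyspnea and fatigue "will also be measured both before and after 6MWT, to evaluate their changes in both the groups". The Specific objectives separate a resting SpO2 from a post-walk one and give the purpose of the latter: "To measure the both the SpO₂ and level of dyspnea and fatigue again after 6MWT, for the assessment of their exercise tolerance at baseline". Later objectives repeat these measurements at weeks 13 and 26.

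The paragraph before the sample size calculation defines the first set of means as those "at resting condition (before 6MWT" and creates a parallel post-walk set: "Similarly after 6MWT all these six subgroups will be again designated as" A0after to B2after. The Data Schedule (Appendix-II) has Before and After columns for SpO2 at days 0, 90 and 180. It has no field for the time of the reading.

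The only oximetry method is the section Test procedure for pulse oximetry. It starts with "The patient will be asked to take rest and remain calm and quiet for 10 minutes". The sensor is then applied, and the section ends: "Three (3) consecutive readings at 5 minutes interval will be taken and the best value will be noted". It does not say which of the two SpO2 values it covers. The section Procedure for six minute walk test (6MWT) describes the course, the encouragement, the stopping signs and the end of the test. It mentions no oximeter, no lowest value during the walk and no time for a post-walk reading.

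**The concern.** A post-walk SpO2 carries information about exercise only if it is read before saturation recovers. A procedure that first imposes rest and then keeps the most favourable of several spaced readings selects against the fall that the measure is meant to detect. The best-of-three rule matches the one used for spirometry, where it suits an effort-dependent manoeuvre. It does not suit a quantity that is recovering over time.

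At stake is the before-to-after SpO2 change, and any difference between arms in that change. If the after value is close to a second resting value, a vitamin D effect on exertional desaturation would be hard to see, and a null result on this item would say little. Later analysis cannot repair this, because an end-of-walk reading that was never taken cannot be reconstructed.

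**Working it through.** The plan states no figure on this point, so there is nothing to reproduce. The check is timing arithmetic plus an illustrative recovery curve.

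**Inputs from the protocol** (Test procedure for pulse oximetry): 10 minutes of rest; three readings; 5 minutes between readings; the best one kept, taken here to mean the highest.

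**Assumptions, not in the documents:** exponential recovery with half-time h of 1 to 5 minutes, with 10 minutes as a slow case; an illustrative exertional fall of 6 SpO2 points.

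**Step 1, timing after the walk ends.**
- Procedure followed as written: 10, 10 + 5 = 15, and 10 + 2 × 5 = 20 minutes.
- Rest dropped but best-of-three kept: 0, 5 and 10 minutes.

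**Step 2, share of the fall still present at time t:** 2^(−t/h).

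| h (min) | 0 min | 5 min | 10 min | 15 min | 20 min |
|---|---|---|---|---|---|
| 1 | 100% | 3.1% | 0.1% | 0.0% | 0.0% |
| 2 | 100% | 17.7% | 3.1% | 0.6% | 0.1% |
| 3 | 100% | 31.5% | 9.9% | 3.1% | 1.0% |
| 5 | 100% | 50% | 25% | 12.5% | 6.25% |
| 10 | 100% | 70.7% | 50% | 35.4% | 25% |

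**Step 3, recorded fall without reading error.** The highest reading is then the last one.
- As written (20 minutes): at most 6 × 0.0625 = 0.375 points for h up to 5 minutes; 6 × 0.25 = 1.5 points for h = 10.
- Rest dropped (10 minutes): at most 6 × 0.25 = 1.5 points for h up to 5 minutes; 6 × 0.50 = 3.0 points for h = 10.

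**Step 4, with reading error.** This was simulated with 400,000 sets of three readings, independent error SD of 1 or 2 points (assumed), and best-of-three used both before and after the walk. The mean recorded before-to-after fall, out of a true 6 points, was:
- As written: 0.0 to 0.8 points for h of 1 to 5 minutes; 2.0 to 2.1 for h = 10.
- Rest dropped: 0.4 to 2.6 points for h of 1 to 5 minutes; 3.7 to 4.0 for h = 10.

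Reading error softens the masking a little, mainly when the rest is dropped. Part of that is an artefact: with unequal post-walk means, error raises the pre-walk maximum more than the post-walk one.

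**Step 5, the alternative.** A reading as the walk ends has t = 0, and 2^0 = 1, so the whole fall present at that moment is kept.

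**The case against.** The strongest reply is that the oximetry section was meant for the resting value only. It opens with calm rest, it comes before the 6MWT section, and the protocol elsewhere equates rest with the pre-walk state. The Data Schedule also puts post-walk SpO2 in the same After column as dyspnea and fatigue, which fits readings taken together at the end of the walk. Both procedures cite the same 2018 source, which may give a post-walk time and is not available here.

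Part of this stands. No sentence in the protocol expressly orders the rest and best-of-three steps after the walk, so a reader should not infer that the plan prescribes a recovered reading or that this is what staff will do. The point rests on this being the only, unqualified procedure for a value that is due twice. If the resting-only reading is right, the post-walk value has no stated time, number of readings or selection rule, and the same repair is needed.

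Three other inferences go too far:
- That exertional desaturation could not be seen at all. The recovery speed and the 6-point fall are assumptions, and with a 10-minute half-time 25% of the fall is still there at 20 minutes.
- That choosing the best of three adds a further upward bias to the results. With the same rule before and after and recovery nearly complete, that bias largely cancels in the change. It also largely cancels between arms.
- That the exercise-tolerance conclusion as a whole is compromised. The Project Summary assesses exercise tolerance by change in 6MWD, with SpO2 and the Borg scores measured in addition.

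**Conclusion.** The point holds as a statement about the procedure as written: the only SpO2 method would also apply after the 6MWT and would largely mask exertional desaturation. For assumed half-times of 1 to 5 minutes, 0% to 25% of the fall remains at the first reading (10 minutes) and 0% to 6% at the last (20 minutes). For a 10-minute half-time the figures are 50% and 25%. If the rest is skipped but the best of three is kept, masking is weaker, though the rule still favours the most recovered reading. The size depends on recovery speed, which the documents do not give; the direction does not.

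The harm is attenuation of one exercise-tolerance item. The procedure is the same in both arms, so it does not favour either. It leaves 6MWD, Borg scores, spirometry and the sample size calculation unaffected. It should be corrected, but it does not threaten the trial's main comparisons.

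**What to change.** In the oximetry section, limit the 10-minute rest and the best-of-three rule to the before-6MWT (resting) value. Add a step at the end of the 6MWT section: apply the sensor as the walk ends, or leave it on if the device allows; record one SpO2 reading immediately, with no rest and no selection among readings; and note the time. Use the same rule at day 0, week 13 and week 26, and add a time field to the After column of the Data Schedule.

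The cost is one procedure paragraph and one form field. It needs no extra visits and no change in sample size. The oximeter model is not stated, so the fix should not depend on a device that can be worn during the walk; applying the sensor at the end avoids that. The downside is that a single post-walk reading is slightly noisier than a repeated one.
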